# • Study Objectives

#### Aims

The overarching aim of the current study is to develop a 2-minute walk treadmill test to evaluate dyspnea. The primary aims are to assess:

- i. the relationship between 6MWD and exertional dyspnea scores within a 6MWT when compared against exertional dyspnea scores recorded during the dyspnea challenge.
- ii. the sensitivity of the dyspnea challenge to changes in exertional dyspnea via changes to the gradient of the treadmill.
- iii. Compare the exertional dyspnea response to the dyspnea challenge in heart failure, pulmonary hypertension and COPD.
- iv. To assess the responsiveness of the dyspnea challenge to changes in exertional dyspnea experienced post an acute intervention and exercise rehabilitation programs (Pulmonary and Heart Failure rehabilitation programs).

Secondary aims, of the study, will be:

- v. To compare the metabolic cost of the 6MWT and the dyspnea challenge.
- vi. To compare the metabolic cost of the dyspnea challenge between cardiopulmonary disease populations.
- vii. Establish a minimally important difference (MID) for the dyspnea challenge.

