## d. Study Procedure

Participants may be required to complete all three parts of this study, there are a total of nine visits over the three parts. Visits 1-3 will address question one and investigate the ability of the 6MWT and its outcome measure of six-minute walk distance (6MWD) to act as a surrogate measure of exertional dyspnea (ED). The secondary outcomes are to non-invasively monitor cardiopulmonary factors to compare the metabolic costs of both tests and compare this across disease population. Visits 4-6 will address question two and consider the sensitivity of the dyspnea challenge in heart and lung disease groups by asking individuals to perform the dyspnea challenge at differing gradients ranging from 3 to 8%. Visits 7-9 will address question four and secondary aim seven to assess the responsiveness of the dyspnea challenge in heart and lung disease groups by asking individuals to perform the dyspnea challenge pre and post an intervention that has proven to increase or decrease dyspnea. There will be an acute challenge using a chest wall binder that will be applied only to COPD participants which is known to increase dyspnea and then a longer term intervention being that of Pulmonary and Heart Failure Rehabilitation which is known to improve dyspnea in the COPD and HF populations. Participants will complete two dyspnea challenges pre and post the exercise rehabilitation programs which will be completed outside of this study. Participants included in the acute challenge part of the study will complete the dyspnea challenge in random order on two separate visits with and without a chest wall binder fitted.

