#### Part C:

Visit 7 and 8 (COPD Participants Only) – Will be completed prior to commencing Pulmonary or Heart Failure Rehabilitation programs (chronic intervention, Figure 1) and the wearing of chest wall binders will only be completed by COPD participants (acute intervention, Figure 1). During these visits participants will be asked to complete 2x DCs per visit. Each test will be completed wearing a forehead oximeter to measure heart rate, rhythm and arterial oxygen saturation. Two of the four DC tests participants will wear a chest wall binder. These four tests will be performed in a random order. At the end of each test participants will be asked to complete the MDP.

Visit 9 – Will be completed after the completion of Pulmonary or Heart Failure Rehabilitation programs by participants. During this visit participants will be asked to complete 2xDC. Each test will be completed wearing a forehead oximeter to measure heart rate, rhythm and arterial oxygen saturation. At the end of each test participants will be asked to complete the MDP and TDI questionnaires.

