#### e. Outcome Measures

## 1. Primary outcome measure:

- a. Dyspnea (ED) -
  - Modified Borg 0-10 Scale A common measure taken during field-based testing. This will be measured using a 0-10 scale and does not involve any invasive procedures. This 0-10 scale has been used previously within COPD patients during the dyspnea challenge[25].
  - Multidimensional Dyspnea Profile (MDP): The MDP contains 11 items which participants rate on a continuous scale (0-10) and a forced-choice question for five sensory qualities [31]. The profile is split into three subsections; Sensory Dimension (SQ), Breathing Discomfort (A1) and Emotional Response (A2)[30]. This has been previously validated within clinical settings[32].
  - *Dyspnea*-12: A 12 descriptor item questionnaire that provides an overall score for breathlessness severity that matches the participants breathing 'these days'. It incorporates seven physical items and five affective items. Frequently used at baseline and during follow-up assessments[33].
  - Baseline and Transition Dyspnoea Index (BDI/TDI): The BDI/TDI measures the severity of breathlessness at the beginning of an intervention (BDI) then again at the end of the intervention (TDI). The questionnaire is comprised of three subsections; Functional Impairment, Magnitude of Task and Magnitude of Effort. This has been previously validated within clinical settings[34].

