## f. Data Analysis

As subjects act as their own controls, a repeated measures Analysis of Variance statistic will be used for quantitative (physiological) data. All tests will be of a 2-within factor design: time and experimental condition. Dyspnea scores will be measured in the same way. Any non-normal distributed data, highlighted by variance ratio tests, will have a non-parametric Kruskal-Wallis test being applied. Post-hoc analysis will be conducted on any statistically significant data identified post study. Questionnaire data will be analyzed using a Wilcoxon signed rank test. For other comparisons, descriptive statistics alone will be used. Data may be further explored using appropriate parametric or non-parametric correlation statistics. All statistical tests will be done with SPSS software with a significance threshold of P<0.05.

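### Visit 9 has the TDI completed after each of two dyspnea challenges, although the protocol ties it to the end of the intervention: two ratings, no rule for which counts, and a risk of carry-over from the breathlessness just provoked

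*Protocol*

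**What the plan says.** Protocol, Methods d. Study Procedure, Part C, places Visit 9 after rehabilitation ("Will be completed after the completion of Pulmonary or Heart Failure Rehabilitation programs by participants"). On the tests it says "During this visit participants will be asked to complete 2xDC", and on the questionnaires "At the end of each test participants will be asked to complete the MDP and TDI questionnaires".

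For Visits 7 and 8, before rehabilitation, the same section names the MDP alone: "These four tests will be performed in a random order. At the end of each test participants will be asked to complete the MDP".

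The outcome section (e. Outcome Measures, primary outcome measure) lists the BDI/TDI among the dyspnea measures and describes it by reference to the intervention: "The BDI/TDI measures the severity of breathlessness at the beginning of an intervention (BDI) then again at the end of the intervention (TDI".

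The opening of d. Study Procedure gives the purpose of these visits: "Visits 7-9 will address question four and secondary aim seven to assess the responsiveness of the dyspnea challenge". Secondary aim vii is "Establish a minimally important difference (MID) for the dyspnea challenge". On analysis, f. Data Analysis says only "Questionnaire data will be analyzed using a Wilcoxon signed rank test".

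**The concern.** The MDP and the TDI have different reference periods. The protocol uses the MDP to rate the exercise test just finished, so completing it after every test is correct. The TDI, by the protocol's own description, belongs to the end of a rehabilitation programme. At Visit 9 the two share one sentence, and the TDI takes on the MDP's timing.

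Two things follow. A site that obeys the text records two TDI values per participant on one day, with nothing to say which is used. Each value is also given after a test designed to make the participant breathless, so the answer about the whole programme may be coloured by that test.

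The second matters most if the TDI serves as the external criterion against which change in the challenge score is judged. Criterion and challenge score could then share error, and the estimates of responsiveness and of the minimally important difference could be biased. An analysis plan could choose between the two ratings, but it could not undo the state in which both were taken.

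**Working it through.** The protocol gives no figure for the TDI, responsiveness or the minimally important difference, so there is nothing to reproduce. The check is a count, a comparison of sections, and a test of whether the bias can be sized.

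**Count.** Challenges at Visit 9: 2. TDI completions per challenge: 1. Ratings per participant: 2 × 1 = 2. A measure taken at the end of one intervention needs 1. If all 30 COPD and 30 heart failure participants reached Visit 9 (assuming no dropout and no pulmonary hypertension participants in this part), that is 60 × 2 = 120 ratings instead of 60.

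**Sections side by side.**
- After-test completion is the protocol's standing rule for the MDP in Parts A, B and C. Visit 9 is the only place where the TDI is attached to it.
- The outcome section locates the BDI at the start of the intervention and the TDI at its end. It mentions no exercise test.
- Of the questionnaires scheduled in Part C, the TDI is the only one that refers to the programme as a whole. Dyspnoea-12 is scheduled at Visit 1 only.
- The BDI is scheduled at no visit. Visit 1 lists the SGRQ or Kansas City questionnaire, mMRC, Dyspnoea-12 and HADS; Visits 7 and 8 list the MDP.
- The protocol accepts elsewhere that test conditions can alter dyspnea ratings: at Visits 2 and 3 it repeats tests without the gas-exchange measurement to remove the effect of the face mask.

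**Can the bias be sized?** Only with assumed inputs. Let D be change in the challenge score, A the TDI without carry-over, and S the breathlessness left by the test, each with variance 1. Let the recorded TDI be A + kS. Then

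corr(D, A + kS) = [corr(D,A) + k·corr(D,S)] / √[1 + k² + 2k·corr(A,S)].

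Assume corr(D,A) = 0.30 and corr(A,S) = 0.2.

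| k | corr(D,S) | Calculation | Observed correlation |
|---|---|---|---|
| 0.25 | 0.6 | 0.45/√1.1625 | 0.42 |
| 0.50 | 0.6 | 0.60/√1.45 | 0.50 |
| 0.50 | 0.1 | 0.35/√1.45 | 0.29 |
| 0.50 | 0 | 0.30/√1.45 | 0.25 |

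At k = 0.50 the correlation rises above 0.30 only if corr(D,S) exceeds (0.30 × √1.45 − 0.30)/0.50 ≈ 0.12. The formula shows how shared error would act. It does not fix a direction, and the protocol supplies none of the inputs.

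**The case against.** The strongest reply is that the sentence may be loose drafting. It is the usual MDP sentence with the TDI added, and one TDI at the end of the visit may be all that was meant. That is possible, but no other section says so, and sites will follow the text. A single TDI after both challenges would still follow provoked breathlessness.

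Second, the outcome section does not say in words that the TDI is given once, and the Visit 9 text gives no interval between the end of a test and the questionnaire. Both are true. The section nonetheless ties the TDI to the intervention and not to a test, and no rest period before the questionnaire is required at Visit 9.

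Third, a reader might infer that the schedule contaminates the anchor for responsiveness and the minimally important difference and so inflates the result. The document does not support that. No section names the TDI as anchor or gives a method for aim vii, and the method may be in an analysis plan that is not shown. The role is plausible: the TDI is the only Part C questionnaire about the whole programme, and the reference cited for it (34) is, by its title, about the smallest important difference on the TDI. Plausible is not stated, however. Carry-over is a risk and not a demonstrated effect, and with other inputs the correlation falls.

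Fourth, moving the TDI ahead of the challenge has its own drawback: asking about improvement first could prime the challenge ratings that follow. This stands as a small cost.

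**Conclusion.** The point holds as a conflict over timing. As written, Visit 9 yields two TDI ratings per participant, each after a provoked-breathlessness test, for a measure that the protocol attaches to the end of the intervention, with no rule for which counts. This rests on the text alone, read literally.

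The consequence for aims iv and vii is conditional. It requires that the TDI be used as the anchor and that the breathlessness just provoked affects the answer. Neither is established, and no size or direction can be given. Even without an anchor role, a listed primary dyspnea measure would be collected under conditions that suit a different instrument. That justifies a correction before Visit 9 data are collected; it does not show that the trial's conclusions would be wrong.

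**What to change.** Amend the Visit 9 text in Part C so that the TDI is completed once, at rest, before the first dyspnea challenge of that visit, and only the MDP is completed at the end of each challenge.

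In the same amendment, schedule the BDI once before rehabilitation for every participant who will go on to Visit 9, since the TDI refers back to it, and state whether the TDI is the anchor for responsiveness or the minimally important difference.

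The timing change is one sentence and removes one questionnaire completion per participant; the BDI adds one. The remaining downside is a small possible priming of the Visit 9 challenge ratings. Ratings already taken after a challenge cannot be repaired later, so the amendment should precede further Visit 9 collection.

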#### e. Outcome Measures

## 1. Primary outcome measure:

- a. Dyspnea (ED) -
  - Modified Borg 0-10 Scale A common measure taken during field-based testing. This will be measured using a 0-10 scale and does not involve any invasive procedures. This 0-10 scale has been used previously within COPD patients during the dyspnea challenge[25].
  - Multidimensional Dyspnea Profile (MDP): The MDP contains 11 items which participants rate on a continuous scale (0-10) and a forced-choice question for five sensory qualities [31]. The profile is split into three subsections; Sensory Dimension (SQ), Breathing Discomfort (A1) and Emotional Response (A2)[30]. This has been previously validated within clinical settings[32].
  - *Dyspnea*-12: A 12 descriptor item questionnaire that provides an overall score for breathlessness severity that matches the participants breathing 'these days'. It incorporates seven physical items and five affective items. Frequently used at baseline and during follow-up assessments[33].
  - Baseline and Transition Dyspnoea Index (BDI/TDI): The BDI/TDI measures the severity of breathlessness at the beginning of an intervention (BDI) then again at the end of the intervention (TDI). The questionnaire is comprised of three subsections; Functional Impairment, Magnitude of Task and Magnitude of Effort. This has been previously validated within clinical settings[34].

# b. Functional capacity

• Six-minute walk distance (6MWD): the maximum distance walked in six minutes during the six-minute walk test (6MWT). The 6MWT is used routinely in clinical settings due to its simplicity and relatively short execution time. This will be conducted at either the Prince Charles Hospital or Griffith University by a physiotherapy clinician or exercise scientist.

## 2. Secondary outcome measures:

- c. Exercise capacity
  - Cardiopulmonary factors Metabolic data will be collected during one 6MWT and one Dyspnea Challenge. All tests will be completed under supervision by an exercise scientist, medical professional and/or qualified physiotherapist.

# d. Central Hemodynamic responses

• *Physio Flow:* during both the 6MWT and dyspnea challenge Q, HR and SV will be recorded continuously at rest, exercise and in recovery by the Physio Flow device at a frequency of 5s. Six electrodes will be placed on all subjects, two on the eft carotid (Z1 and Z2), two in the breast area (EKG1 and EKG2) and two in the chest area (Z3 and Z4 – EKG3). The validity of the Physio Flow in a COPD population has been shown previously [35]

## e. Impact of disease

- St. George Respiratory Questionnaire (SGRQ): is a reliable and valid measure of quality of life within a COPD population. It is a 50-item questionnaire that has two parts. Part 1 assesses the frequency and severity of symptoms with a 1,3 or 12month recall period. Part 2 refers to the activities that cause or are limited by breathlessness. These will be performed at both sites during the study.
- Kansas City Cardiomyopathy Questionnaire (KCCQ-12): has validity and sensitivity to capture the impact of heart failure on patients' lives and is strongly associated with clinical events over time. It has a 2-week recall period on symptoms associated with heart failure. Includes 7 domains; symptom frequency, symptom burden, symptom stability, physical limitations, social limitations, quality of life and self efficacy.

## f. Skeletal muscle oxidative capacity

• Near-infrared spectroscopy (NIRS): is a non-invasive and fairly inexpensive method for measuring skeletal muscle blood flow and oxidative metabolism [36]. Measurements on the vastus lateralis muscle will be performed as previously described [37]. This will be conducted at the exercise testing laboratory in GO2 building at Griffith University's Gold Coast campus.

## f. Data Analysis

As subjects act as their own controls, a repeated measures Analysis of Variance statistic will be used for quantitative (physiological) data. All tests will be of a 2-within factor design: time and experimental condition. Dyspnea scores will be measured in the same way. Any non-normal distributed data, highlighted by variance ratio tests, will have a non-parametric Kruskal-Wallis test being applied. Post-hoc analysis will be conducted on any statistically significant data identified post study. Questionnaire data will be analyzed using a Wilcoxon signed rank test. For other comparisons, descriptive statistics alone will be used. Data may be further explored using appropriate parametric or non-parametric correlation statistics. All statistical tests will be done with SPSS software with a significance threshold of P<0.05.

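### The prescribed two-within-factor ANOVA contains no disease group, so primary aim iii and secondary aim vi get no planned test, and the association in primary aim i rests on an optional correlation

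*Protocol*

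**What the plan says.** The Aims section of the protocol lists aims i to iv as primary. Aim i concerns "the relationship between 6MWD and exertional dyspnea scores within a 6MWT when compared against exertional dyspnea scores recorded during the dyspnea challenge". Aim iii is to "Compare the exertional dyspnea response to the dyspnea challenge in heart failure, pulmonary hypertension and COPD". Secondary aim vi makes the same cross-disease comparison for metabolic cost. Hypothesis i is directional: a longer walk distance goes with less dyspnea in the six-minute walk test (6MWT). The Study Population section plans 30 participants in each disease group.

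The section f. Data Analysis then sets the methods:

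- Physiological measurements get a repeated measures ANOVA, on the ground that each person is their own control.
- The design of that analysis is fixed: "All tests will be of a 2-within factor design: time and experimental condition".
- For the primary outcome: "Dyspnea scores will be measured in the same way".
- Non-normal data "will have a non-parametric Kruskal-Wallis test being applied"; no grouping factor is named.
- Questionnaires get a Wilcoxon signed rank test.
- The rule for whatever is left over: "For other comparisons, descriptive statistics alone will be used".
- Association appears only as an option: "Data may be further explored using appropriate parametric or non-parametric correlation statistics".

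**The concern.** Each participant has one disease, so disease group is a between-participant factor. Nobody acts as their own control for it, and it is neither time nor experimental condition. A plan limited to those two factors cannot test a disease difference, and the residual rule then sends that comparison to description. Aim i has a related problem. It asks how walk distance varies with dyspnea across people, while the prescribed ANOVA compares mean scores within people. The only listed method that estimates an association is optional.

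At stake are the between-disease conclusion, which is one of four primary aims, and the evidence on whether walk distance can stand in for dyspnea. If these analyses are chosen only once the data are in, the choice of test, of dyspnea score and of how to treat the three diseases could follow the results.

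**Working it through.** The protocol states 90 participants but no SD, effect size or power, so there is no figure of its own to reproduce. The check is mainly structural.

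**Aims against methods**

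- Aim ii (gradient) and the before-after or with-without contrasts of aim iv are within participants. The ANOVA fits.
- Aim i, 6MWT scores against challenge scores: a within-participant condition contrast. The ANOVA covers it, although the 6MWT is rated on the modified Borg scale and the challenge on a numerical rating scale (Study Procedure, Part A).
- Aim i and hypothesis i, walk distance with dyspnea: a between-participant association. Reassign the walk distances among participants at random. The ANOVA of dyspnea scores does not change, but the correlation does. The ANOVA therefore carries no information on this question.
- Aims iii and vi: reassign the disease labels among participants at random. A model with only time and condition gives the same result. It carries no information on disease differences.

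**Other listed methods**

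- Kruskal-Wallis compares independent groups, but it is offered only where data are non-normal and names no disease factor. Normally distributed data would still have no between-disease test.
- Wilcoxon signed rank is a paired test and cannot compare diseases.
- Correlation fits aim i but is left open as further exploration.

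**Where disease differences go in the ANOVA**

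A stable difference in level between diseases is part of the participant term and is removed from the within-participant error. Only a disease-by-condition or disease-by-time interaction enters that error.

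**Illustrations (the SD, spacings, pooling and power are assumptions)**

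1. Precision for aim iii. Assume an SD of 2 units on the 0-10 scale, with 30 per group. The 95% CI half-width for one pairwise difference is 1.99 × 2 × √(2/30) = 1.03 units.
2. Detectable pairwise difference, with two-sided 5% and 80% power: (1.96 + 0.84) × √(2/30) = 0.72 SD.
3. Pooled correlation for aim i. Assume no correlation within any disease, unit within-group SDs, equal groups, and disease means at −d, 0 and +d SD on one variable and in the reverse order on the other. Then r = −(2d²/3) / (1 + 2d²/3).
   - d = 0.5: −0.167/1.167 = −0.14.
   - d = 1: −0.667/1.667 = −0.40.
4. Detectable correlation with all 90, at 80% power by Fisher's z: tanh(2.80/√87) = 0.29. The artefact at d = 1 exceeds this and has the sign that hypothesis i predicts. The one at d = 0.5 does not reach it.

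**The case against.** The strongest reply has four parts.

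- The section lists more than one method. This stands: Kruskal-Wallis, Wilcoxon and correlation are all named. A reader might infer that every analysis is fixed as the two-within-factor ANOVA, and the text does not support that. The rule binds the physiological data and dyspnea scores, and none of the other methods supplies a planned disease comparison.
- Aim iii may be meant descriptively. None of the four hypotheses concerns a difference between diseases, and the section on translation to practice restates only two primary aims, neither of them the disease comparison. This has some weight: description would be a weak choice, not an invalid one. But the Aims section lists the comparison as primary with 30 per group, and nothing says that description was intended for it.
- Aim i is partly covered, and the right family of methods is named. Both are true. What remains is that the association in a primary aim, with a directional hypothesis, depends on an analysis that need not be done.
- Details belong in a statistical analysis plan. A plan could add the adjustment for disease. To supply the missing test, however, it would have to overrule the protocol's statements on the design of all tests and on the remaining comparisons.

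Two stronger readings are tempting and should not be drawn. One is that omitting disease inflates the ANOVA error through differences in disease level; those go to the participant term. The other is that the protocol will pool all 90 people in an unadjusted correlation. It does not say so, and it refers elsewhere to separate heart and lung disease groups.

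**Conclusion.** The point holds as a conflict between a stated analysis rule and the protocol's own aims. As written, primary aim iii and secondary aim vi have no planned inferential comparison, and the association in primary aim i and hypothesis i has only an optional one. The within-participant part of aim i is covered. This conclusion rests on the text alone and needs no assumed figure.

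The size of the loss cannot be derived from the protocol. The ±1.03 units depends on an assumed SD of 2. The −0.14 and −0.40 depend on pooling, on the assumed spacings and on disease means running in opposite directions. They show that 30 per group can support an estimate with an interval, and why a correlation across diseases should be adjusted. They do not show a bias that the plan is known to have.

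**What to change.** Amend section f. Data Analysis before any analysis:

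- **Aims iii and vi.** Add disease group as a between-participant factor, in a mixed ANOVA or a mixed model, for dyspnea challenge outcomes. Estimate the disease contrasts within the challenge, each with a 95% CI. A disease effect averaged over the 6MWT and the challenge would not answer these aims and would combine two rating scales. Add disease-by-time or disease-by-gradient interaction where relevant. For aim vi, use the challenge in which gas exchange is measured.
- **Aim i.** Make the correlation of walk distance with end-of-test dyspnea a planned main analysis, once for the 6MWT and once for the dyspnea challenge, both from the tests done without the face mask. Adjust each for disease group and give a 95% CI. Keep the within-participant contrast of the two tests as it is, and acknowledge the two scales.
- **Residual rule.** Exempt these aims from the description-only sentence.

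The cost is a few lines of text. The tests with and without the mask and the dyspnea ratings are already planned in Part A, so no new visit or measurement is needed.

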The DC will be performed be on a treadmill in a temperature-controlled laboratory. Participants will walk on a treadmill for 2-minutes at a speed of 3km/h and a gradient of 4%. Perrault *et al.*, [17] found that 93% of patients suffering from moderate-severe COPD managed to complete a 3-minute walk test at 1.5km/h on a flat surface and that only 84% managed to complete the test at 2.5km/h. The gradient selected was chosen as previous research in 8 participants with mild COPD managed to achieve a 2-minute challenge at between 4-6% gradient[25]. Electrocardiogram (ECG), Heart rate (HR) and oxygen saturation (SpO2) will be monitored continuously using a portable saturation monitor (RAD-5v Masimo Corp, Irvine, CA, USA). Ratings of ED will be participant self-reported every 10 seconds using a 0-10 Numerical Rating Scale (NRS) on a PC-based system with a computer monitor mounted in front of the treadmill. Pulmonary gas exchange (Metamax, Cortex BXB, Lepzig, Germany), cardiac output (Q) (PhysioFlow, Manatec Biomedical, Paris, France) and muscle tissue oxygen saturation (MtO2) (PortaMon Artinis Medical Systems, Einsteinweg, The Netherlands) will be monitored continuously. At the end of the test, sensory and affective measures of ED will be assessed using the MDP[30].

Visit 2 and 3 – During these two visits, participants will perform 2x6MWT and 2xDC. These tests will be performed in a randomised order with 30 minutes of rest in between. 1x6MWT and 1xDC will be performed as above with the same equipment and measures assessed. The other two tests they will be performed without the pulmonary gas exchange measures being assessed. This is to negate the impact of the face mask on self-perceived ratings of exertional dyspnea. During these two tests, ECG, Q, MtO2, HR, SpO2, and blood pressure will be monitored as above. At the end of each test the MDP will be performed.

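### The fixed time-by-condition repeated measures ANOVA needs every cell filled, so by default a participant with one truncated challenge or missed visit leaves that Part's rating-over-time analysis

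*Protocol*

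**What the plan says.** Under f. Data Analysis the protocol states that "a repeated measures Analysis of Variance statistic will be used for quantitative (physiological) data". It then gives the design and extends it to the symptom ratings: "All tests will be of a 2-within factor design: time and experimental condition. Dyspnea scores will be measured in the same way". The verb is loose, but the only sensible reading is that dyspnea ratings are analysed by the same ANOVA. The software and threshold are also fixed: "All statistical tests will be done with SPSS software with a significance threshold of P<0.05". A Kruskal-Wallis test replaces the ANOVA when data are not normal. Questionnaires go to a Wilcoxon signed rank test, and correlations are allowed.

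Under d. Study Procedure, the challenge lasts 2 minutes and dyspnea is rated every 10 seconds (Parts A and B). Part B has six challenges at gradients of 3-8%, spread over visits 4 to 6. Part A tells participants the criteria for ending a test early. It also cites an external paced-walk study in moderate-severe COPD in which 93% completed 3 minutes on the flat at 1.5 km/h and "only 84% managed to complete the test at 2.5km/h". Of this study's own challenge Part A says: "Participants will walk on a treadmill for 2-minutes at a speed of 3km/h", on a 4% gradient. The section on participant withdrawal allows people to leave at any time. The protocol does not say how a truncated test or a missed visit enters the ANOVA, and it does not define the levels of *time*.

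**The concern.** The protocol commits to a method that fits poorly with the data it expects to collect. A classical ANOVA with two within-subject factors works on a full grid of participant by time by condition. In SPSS's repeated measures procedure, a participant with any empty cell is removed from that model. The Kruskal-Wallis fallback does not help, because it is triggered by non-normality and not by gaps.

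The challenge is built to provoke breathlessness, so it is plausible that those who stop early are among the more breathless. If so, the rating-over-time analysis would rest on people who tolerate the test. Two consequences would follow in Part B: dyspnea levels would be too low, and the effect of gradient, which is a primary aim, would be somewhat too small. With 30 participants per disease, the loss of precision also matters.

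**Working it through.** The protocol gives no power calculation, dropout rate or expected number of completers, so there is no figure of its own to reproduce. What follows is illustration from its stated design and cited rates.

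**1. Size of the grid.** If each 10-second rating is a level of *time*, one challenge gives 120/10 = 12 ratings and Part B gives 6 × 12 = 72 cells per participant. Fewer levels mean fewer cells, but a stop before the last level still leaves a gap. The exception is an end-of-test value defined as the last rating whenever the test ends.

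**2. Does the method need a full grid?** Ten simulated participants × 12 times × 6 conditions give 720 values. With one value removed, a standard two-within-factor repeated measures ANOVA routine (in Python, not SPSS) rejected the data as unbalanced.

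**3. Share of participants lost from a six-test analysis.** Let p be the completion rate per test, taken as 0.93 or 0.84 from the cited walk.

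- Same people always stop: loss = 1 − p.
- Independent stops: loss = 1 − p^6, so 1 − 0.93^6 = 0.353 and 1 − 0.84^6 = 0.649.
- Correlated stops (equicorrelated probit with correlation ρ): loss = 1 − ∫ φ(u) Φ[(z − √ρ·u)/√(1 − ρ)]^6 du, where z = Φ⁻¹(p). The assumed ρ = 0.85 is close to the value implied by the SDs in step 4: 1.7²/(1.7² + 0.7²) = 2.89/3.38 = 0.855.

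| Pattern of stopping | p = 0.93 | p = 0.84 |
|---|---|---|
| Same people always stop | 7% (2.1 of 30) | 16% (4.8 of 30) |
| Correlation 0.85 | 15% (4.5 of 30) | 30% (9.0 of 30) |
| Independent | 35% (10.6 of 30) | 65% (19.5 of 30) |

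The 93% rate was seen at the speed that Part B states (1.5 km/h), but on the flat and over 3 minutes. The 84% rate was seen at a faster speed.

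**4. Direction and size of bias if stopping follows breathlessness.** All inputs here are assumptions: 200,000 simulated people, mean rating 4, between-person SD 1.7, residual SD 0.7, average slope 0.5 points per 1% gradient with slope SD 0 to 0.3, and a test counted as stopped when the rating reaches 6, 7 or 8.

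- Complete on all six tests: 59% to 92%.
- Mean rating in completers: 2.96 to 3.73 against 4.0 in everyone, so 0.27 to 1.04 points too low.
- Gradient slope in completers: from 0.495 against 0.500 (1 − 0.495/0.500 = 1%) to 0.435 against 0.505 (1 − 0.435/0.505 = 14%).

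The 14% end goes with a stop at a rating of 6, where only 65% complete the steepest gradient. With stops at 7 or 8, where 81-93% complete it, the slope bias is 1% to 9% (largest case 1 − 0.463/0.508 = 9%).

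**The case against.** The strongest reply is that exclusion is inferred. The protocol names a family of tests and a software package, and states no deletion rule. A peak-at-stop or carry-forward rule would keep early stoppers in the same ANOVA, and such a rule could sit in an analysis plan that is not shown. This stands as far as it goes: deletion is the method's default and not a stated rule. It does not remove the point, because the method is fixed in the protocol and handles expected gaps badly. Carrying forward a rating that is still rising would also understate dyspnea in the same people.

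Several stronger readings are tempting and the documents do not support them:

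- *That all dyspnea analyses lose these people.* The MDP is completed after each test, questionnaires go to the Wilcoxon test, and correlations are allowed. None of these needs the time grid. A participant leaves at most the time-course model of that Part.
- *That 72 cells per person is the planned analysis.* The levels of *time* are not defined.
- *That the most breathless are known to be the ones lost.* Reasons for stopping are not documented, and safety criteria need not track the rating.
- *That a third to two thirds will be lost.* This needs independent stops, which conflicts with the idea that the same breathless people stop.
- *That binder and rehabilitation effects are biased by a known amount.* The Part C text does not restate the 10-second ratings.
- *That the cited completion rates apply here.* They come from a flat walk in COPD. The protocol's direct evidence on the challenge is more favourable: 8 participants with mild COPD completed it at 4-6%, and the pilot work was judged safe and repeatable. That evidence is small and from mild disease.

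**Conclusion.** The point holds in a limited form. The protocol fixes a method that needs complete data for the rating-over-time and physiological time-course analyses, while it foresees early termination and allows withdrawal across a multi-visit design. By default, one truncated challenge or one missed visit removes a participant from that Part's model.

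The illustrative loss over six Part B tests runs from 7-16% (fully dependent stops), through about 15-30% (correlation 0.85), to 35-65% (independent stops). It rests on borrowed completion rates. The first two patterns fit better with stopping as a personal characteristic. If stopping is related to breathlessness, dyspnea levels are understated and the gradient effect is reduced by about 1-14%. Those figures depend wholly on the assumed means, SDs and stop limits. The level bias is the clearer of the two. This is worth correcting before analysis, but it does not invalidate the study's other dyspnea measures.

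**What to change.** In f. Data Analysis, replace the two-factor repeated measures ANOVA for dyspnea ratings over time and physiological time courses with a linear mixed model (SPSS MIXED) that uses every recorded value. Include time and condition as fixed effects, participant random effects and a serially correlated residual. Define the levels of *time*.

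State that the model assumes stopping depends on data already observed (missing at random). This is an assumption and not an established fact: an unrecorded jump in dyspnea at the moment of stopping would violate it. Report the number and timing of early stops by condition beside the dyspnea result, so that readers can judge it. Keep the completers-only ANOVA as a sensitivity analysis.

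The cost is a change of wording, slightly more analysis work and reliance on the missing-at-random assumption. No new data are needed.
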